For the analysis of systemic glucocorticoid dose tapering, conversion to prednisone-equivalent dose may be required, if different glucocorticoids have been administered. Furthermore, the glucocorticoid dose will be expressed as prednisone-equivalent mg/kg body weight/day.

AD-ST-33.04 Effective date: 30-Jun-2017

Version 2.0 | Date 29-Oct-2020 | AD-PR-109.01 Effective date: 26-Jun-2017

Page 21 of 51

Steps to calculate the prednisone equivalent dose (mg/kg/day):

- 1) Select systemic glucocorticoids where route is IV or oral from the 'Systemic glucocorticoids from SD-3 until SD15' form. Reported doses in the 'Systemic glucocorticoids from SD-3 unit SD15' form are daily doses and the number of doses per day is set to 1.
- 2) Select concomitant medications with ATC code H02B (Glucocorticoids) from the 'Concomitant medication' form with IV or oral route of administration. Calculate the frequency per day as follows (this list should not be seen as exhaustive):

Frequency	Description	Number of doses per day
OB, QD	Once a day	1
BID	Twice a day	2
TIB	Three times a day	3
QID	Four times a day	4
QW	Every week	1/7
2xW	Twice per week	2/7
3xW	Three times per week	3/7
NxW	N times per week	N/7
EVERY 2 WEEKS	Every 2 weeks	1/14
QM	Every month	1/30.4375
QAD	Every other day	0.5
Once	Single intake	1/(stop date – start date +1)
PRN	As needed	0
Other	Other	0
UNK	Unknown	0

AD-ST-33.04 Effective date: 30-Jun-2017

Version 2.0 | Date 29-Oct-2020 | AD-PR-109.01 Effective date: 26-Jun-2017

CI	Continuous infusion	0

Note: Administration of glucocorticoids with 'as needed', 'other', or 'unknown' frequency will not be included in the calculation of the equivalent dose.

- 3) If the dose unit is not mg, then the following conversion will be done: 1 g = 1000 mg, 1 mcg = 0.001 mg. IV and oral routes of administration are equivalent.
- 4) Select the weight in kg from the physical examination visit closest to the glucocorticoids administration date.
- 5) Calculate the equivalent dose of prednisone using the following formula:

Equivalent dose (mg/kg/day)= 
$$\frac{Conversion \ Factor * Dose(mg) * Number \ of \ doses \ per \ day}{Weight \ (kg)}$$

where the conversion factor is:

- 1 for prednisone
- 1.25 for methylprednisolone
- 1 for prednisolone
  - Glucocorticoids tapering = glucocorticoids permanently tapered
    - to the same (or lower) dose being administered before the occurrence of MAS (in patients already on treatment for sJIA/AOSD

or

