• by at least 50% of the equivalent dose of prednisone administered at emapalumab treatment start (in those patients who present with MAS at sJIA/AOSD onset).

The daily equivalent dose of prednisone will be compared with the daily equivalent dose of prednisone at SD0.

AD-ST-33.04 Effective date: 30-Jun-2017

Version 2.0 | Date 29-Oct-2020 | AD-PR-109.01 Effective date: 26-Jun-2017

Page 23 of 51

If it is not possible to establish if a patient has been treated for sJIA/AOSD or not before study start for all patients, or if it is not possible to retrieve glucocorticoids dose administered before the occurrence of MAS for all patients who already are treated for sJIA/AOSD, the glucocorticoids tapering endpoint will be changed. In this case the endpoint will be: "glucocorticoids permanently tapered at any time during the study by at least 50% of the equivalent dose of prednisone administered at emapalumab treatment start (SD0).

If glucocorticoid dosing data are unavailable at a given time point, the assumption that dose has not been further tapered from the previous available observation will be made. Glucocorticoid doses will be calculated as (prednisone-equivalent) mg/kg/day.

- MAS remission = resolution of clinical signs and symptoms according to the Investigator (MAS clinical signs and symptoms score ≤ 1) AND normalization of laboratory parameter relevant to MAS as follows:
  - White blood cell count (WBC) and platelet count above the lower limit of normal (LLN)
  - Lactate dehydrogenase (LDH) below 1.5 upper limit of normal (ULN)
  - Alanine aminotransferase/aspartate aminotransferase (ALT/AST) below 1.5 ULN
  - Fibrogen higher than 100 mg/dL
  - Ferritin level decreased by at least 80% from values at screening or baseline (whichever is higher) or below 2000 ng/mL, whichever is lower

If one or more laboratory data are unavailable within the visit window, the LOCF approach will be used.

- MAS remission by week 8 = patients who meet MAS remission conditions in the period SD56  $\pm$  5 days regardless the time of first MAS remission or its duration.
- Survival:

Time to death = date of death - date of first emapalumab infusion + 1

Patients who survive to the end of the study will be censored at the date of last contact. In case in which a patient withdrew consent the censoring date will be the date of withdrawal of consent.

• Time to MAS remission:

AD-ST-33.04 Effective date: 30-Jun-2017

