#### 9.6. Concomitant Medication

Concomitant medications by ATC level 2 will be summarized descriptively using counts and percentages. Concomitant medication administered for the treatment of sJIA will be also summarized and presented separately.

Concomitant use of biologics will be also summarized and presented separately.

Glucocorticoids administered since the date of MAS diagnosis will be summarized and presented separately as prednisone-equivalent mg/kg/day.

Medications that start prior to initiation of study drug will be considered prior medications, whether or not they were stopped prior to treatment. Any medications that are continuing or start post-dose will be considered to be concomitant. Medications that start prior to initiation of study drug and continue post-dose will be considered both prior and concomitant. If the start/stop dates of a medication are partially or completely missing, then the medication will be assumed to be concomitant if it cannot be definitely shown that it was not administered during the treatment period. Missing dates will not be replaced.

Concomitant medications and systemic glucocorticoids use from SD-3 until SD15 will be presented in separate listings.

Medications will be coded using anatomical therapeutic chemical (ATC) classification level 2 (World Health Organization Drug Dictionary [WHO-DD] Version 2019).

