		"4) Select the weight in kg from the physical examination visit closest to the glucocorticoids administration date. If there are 2 such observations that are equidistant from the glucocorticoids administration date, the first observation will be selected. Prior to first treatment administration, the weight at screening will be selected."
Section 6.1.7 – Derived variables/ Steps to calculate the prednisone equivalent dose (mg/kg/day) and total daily doses	No specification of time frame for calculation of equivalent prednisone dose or total daily doses of anakinra, canakinumab, ciclosporin, etoposide, methotrexate, and tocilizumab.	To add detail on when equivalent daily dose of prednisone, and daily total doses of anakinra, canakinumab, ciclosporin, etoposide, methotrexate, and tocilizumab will be derived.
of anakinra, canakinumab, ciclosporin, etoposide, methotrexate, and tocilizumab		Specifications added: "Equivalent daily dose of prednisone, and daily total doses of anakinra, canakinumab, ciclosporin, etoposide, methotrexate, and tocilizumab will be derived from study day -180 until the end of the study."

[figure not shown]
 Version 2.0
 Date 22-Jul-2021
 AD-PR-109.02
 Effective date: 17-Aug-2020
 Page 8 of 18

Section 6.1.7 - "where the conversion factor is:  Derived 1 for prednisone	The use of dexamethasone was
variables/ Conversion factor for derivation of equivalent dose of prednisone  1.25 for methylprednisolone 1 for prednisolone"	not considered initially and should be added as administered to some patients.  /  Corrected to "where the conversion factor is:
	1 for prednisone
	1.25 for methylprednisolone
	1 for prednisolone 6 for dexamethasone"
Section 6.1.7 - Derived variables/ MAS remission  "The MAS remission evaluation is based on combination of assessments, including Investigator assessment and laboratory finding The latest date of assessments, within the view window of $\pm$ 3 days around the planned day the visit, will be used for the calculation of time to MAS remission."	To clarify assessment handling for the MAS remission. Currently in the SAP, it specifies "If one or more laboratory data are unavailable within the visit window" but no details on the visit windows.  /  Updated to: "The MAS remission evaluation is based on a combination of assessments, including Investigator assessment and laboratory findings, and will only be calculated if the Investigator assessment has been

[figure not shown]
 Version 2.0
 Date 22-Jul-2021

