 AD-PR-109.02
 Effective date: 17-Aug-2020
 Page 9 of 18

	T	<del>-</del>
Section 6.1.7 – Derived variables/ Definition of Biologics	No specification of biologics concomitant used is specified in the SAP version 2.0.	Concomitant use of relevant biologics will be also summarized per section 9.6 however no specification was provided under section 6.1.7.  /  Specifications added: "Relevant concomitant biologics medications will be defined as medications from ATC 4 levels L04AB, L04AC."
Section 6.1.8 - Data Adjustments/Han dling/Convention s/ Handling partial or missing start/stop dates for equivalent daily dose of prednisone, and daily total doses of anakinra, canakinumab, ciclosporin, etoposide, methotrexate, and tocilizumab	No details regarding how to handle partial or missing start/stop dates for equivalent daily dose of prednisone, and daily total doses of anakinra, canakinumab, ciclosporin, etoposide, methotrexate, and tocilizumab	To add detail on how to handle partial or missing start/stop dates for equivalent daily dose of prednisone, and daily total doses of anakinra, canakinumab, ciclosporin, etoposide, methotrexate, and tocilizumab.  /  Imputation of partial/missing medication start or stop dates for equivalent daily dose of prednisone and daily total doses of anakinra, canakinumab, ciclosporin, etoposide, methotrexate, and tocilizumab: -Partial medication end date  • If only month and year are available, medication end date will be imputed to the last day of the corresponding month  • If only year is available, medication end date will be imputed to the 31st of December of the corresponding year -Partial medication start date  • If only month and year are available, medication start date  • If only month and year are available, medication start date

[figure not shown]
Version 2.0 | Date 22-Jul-2021 | AD-PR-109.02 Effective date: 17-Aug-2020 Page 10 of 18

date will be imputed to the
1st day of the
corresponding month
• If only year is available,
medication start date will
be imputed to the 1st of
January of the
corresponding year.
-Medication start and end dates are
both missing, then the record of the
medication will not be considered
(i.e. no derivation of equivalent
dose of prednisone or daily dose of
anakinra,).
-Medication end date is missing
(and medication start date not
missing)
• When medication end date
is missing and "Ongoing" is not ticked
If medication start
date < Study day -
180, then this
record will not be
considered (i.e. no

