Sections 9.6 – Concomitant Medication / Remove of Concomitant Medications Administered for the Treatment of sJIA analysis	"Concomitant Medications Administered for the Treatment of sJIA will be also summarized and presented separately."	A number of medications can be administered to treat both sJIA and MAS. The investigators may record either sJIA or MAS (or both) as indication for their use. A summary table presenting only medications administered to treat sJIA may provide partial and potentially misleading information. All concomitant medications with their reported indications will be presented in listings. It was decided that the following sentence will be removed:  "Concomitant medication administered for the treatment of sJIA will be also summarized and presented separately."

[figure not shown]
Version 2.0 | Date 22-Jul-2021 | AD-PR-109.02 Effective date: 17-Aug-2020 Page 14 of 18

[figure not shown]
Section 9.6 – Concomitant Medication/ WHO-DD version correction	"Medications will be coded using anatomical therapeutic chemical (ATC) classification level 2 (World Health Organization Drug Dictionary [WHO-DD] Version 2019)."	Correction of the WHO-DD version  / Corrected to:  "Medications will be coded using anatomical therapeutic chemical (ATC) classification level 2 (World Health Organization Drug Dictionary [WHO-DD] Version March 2020)."
Section 12.1 – Patient profile report/ Removal of DOB	"Header: subject identification number, sex, study site, date of birth, age at screening."	As described for Section 15.2, Date of birth (DOB) is protected information under the GDPR, therefore the DOB was removed from the patient profile.  /  Corrected to: "Header: subject identification number, sex, study site, age at screening (years)."
Section 14.1, Table 5 – Safety Data/ Remove of Concomitant Medications Administered for the Treatment of sJIA table	Concomitant Medications Administered for the Treatment of sJIA by ATC Level 2 and Preferred Term	As detailed for Section 9.6, the table on Concomitant Medications Administered for the Treatment of sJIA by ATC Level 2 and Preferred Term will be removed.  / Remove Table 14.3.6.2.2 from the list of Tables.

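### Partial steroid dates are imputed to the earliest start and latest stop without regard to known neighbouring dates, so an earlier dose step can overrun a later one and distort the taper endpoints

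*SAP*

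**What the plan says.** The change to Section 6.1.8 in the SAP Errata v2.0 covers partial dates used to derive the daily prednisone-equivalent dose (and the daily doses of six other drugs).

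- Partial stop: "If only month and year are available, medication end date will be imputed to the last day of the corresponding month". With only a year, the "medication end date will be imputed to the 31st of December of the corresponding year".
- Partial start: a month-only start goes to day 1 of that month; a year-only start will "be imputed to the 1st of" January.
- The one limit, in the errata change to 6.1.7, is that doses "will be derived from study day -180 until the end of the study".
- Wholly missing dates are treated differently. A missing start is set to the stop date. A missing stop, when ongoing is not ticked, is set to the start date if the start lies between SD-180 and SD0, and to end of study if the start is on or after SD0.

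SAP 6.1.7 judges tapering on this derived dose. Route (i) is a permanent reduction "to the same (or lower) dose being administered before the occurrence of MAS (in patients already on treatment for sJIA/AOSD". Route (ii) is a permanent reduction of at least 50% from emapalumab start: "The daily equivalent dose of prednisone will be compared with the daily equivalent dose of prednisone at SD0". If prior treatment or the pre-MAS dose cannot be established for all patients concerned, the endpoint falls back to the 50% rule. Time to tapering runs to the date the target is permanently reached. The endpoint of tapering to 1 mg/kg/day or less also requires permanent tapering.

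Steroid data come from a log of daily doses for SD-3 to SD15 and from the concomitant-medication log. The SAP does not say how overlapping records are combined, or which day supplies the pre-MAS dose.

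**The concern.** The rule works record by record. It can give a patient two successive dose steps on the same day even when the later step's start date is fully recorded and shows that the earlier one had ended. The criterion requires that the reduction be permanent, so a stretched higher dose pushes the taper date back for as long as the stretch lasts, or removes the taper altogether.

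Two further effects depend on circumstances. If overlapping steps are summed on SD0, the reference dose rises and the 50% target becomes easier. If a steroid started for MAS carries a month-only start, it moves to the 1st, possibly before MAS occurred, and may then be read as the pre-MAS dose.

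At stake are the tapering proportion, the proportion tapering to 1 mg/kg/day or less, and time to tapering, in about 12 patients.

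**Working it through.** The documents give no figure to reproduce, so the rules were applied literally to hypothetical records. Because the SAP has no rule for overlaps, each was combined both by sum and by maximum. The 2.0 mg/kg/day level matches the minimum background dose in Protocol 6.1. All other doses and all dates are assumptions.

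**Size of the stretch.** If the true day is uniform over an m-day month, the mean shift of a month-only date is (m − 1)/2: 13.5, 14.5 and 15.0 days for m = 28, 30 and 31, with maxima of 27, 29 and 30. A year-only date moves 364/2 = 182 days on average and at most 364, before the SD-180 to end-of-study limit.

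**Known next start, partial stops.** SD0 is 3 June. The steps are 2.0 (true stop 9 June, recorded as June), 1.0 (start 10 June known, true stop 16 June, recorded as June) and 0.5 mg/kg/day (start 17 June known, running to 31 July).

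- SD0 dose 2.0; 50% target 1.0.
- True dates: permanent taper on 10 June = SD7.
- Errata rule: the 2.0 step runs to 30 June = SD27, so permanent taper is on 1 July = SD28. The delay is 30 − 9 = 21 days.
- With time counted as date minus first infusion plus 1, time to taper goes from 8 to 29 days.
- Taking SD-3 to SD15 from the daily log does not repair this if the 2.0 step is also in the concomitant-medication log. It still occupies SD16 to SD27, and the criterion is permanence.
- With a year-only stop on the 2.0 step, and 31 December after the patient's last visit, no taper would be counted.

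**All dates partial in one month.** SD0 is 3 June. The steps are 2.0, 1.5, 1.0 and 0.5; all dates are recorded as June except the last stop, which is July.

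| | SD0 dose | 50% target | Permanent taper |
|---|---|---|---|
| True dates | 2.0 | 1.0 | SD14 |
| Errata, maximum | 2.0 | 1.0 | SD28 |
| Errata, sum | 2.0 + 1.5 + 1.0 + 0.5 = 5.0 | 2.5 | SD28 |

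The delay does not depend on how overlaps are combined. The inflated SD0 reference does: under summing, the true starting dose of 2.0 already lies below the 2.5 target.

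**Pre-MAS target.** Maintenance is 0.2 mg/kg/day. MAS occurs on 20 June, and a 2.0 steroid truly started that day is recorded as June. Its start becomes 1 June, so the dose on 19 June becomes 0.2 + 2.0 = 2.2 (sum) or 2.0 (maximum) instead of 0.2. The target is 10 to 11 times too high, and a patient still on 0.8 mg/kg/day would count as tapered.

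**Effect on the estimate.** 1/12 = 8.3 points. For example, with exact Clopper-Pearson 95% limits, 9/12 = 75.0% (42.8 to 94.5) becomes 10/12 = 83.3% (51.6 to 97.9).

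**The case against.** Nothing in the documents shows that any steroid record has a partial date. Errata v2.0 revises these rules, which suggests such records exist but does not prove it.

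The pre-MAS error needs an unlikely record. The MAS steroid is the eligibility treatment, and Protocol 4.1.1, 6.1 and 8.2 require inadequate response to it to be documented in detail, so a month-only start should be rare. The SAP also does not say that the pre-MAS dose is read from the derived series, and the 6.1.7 fallback removes that target where it applies. These points stand, and they make this part conditional.

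The daily log for SD-3 to SD15 gives actual doses around SD0 and through the early taper. This largely stands: in that period a stretched record does harm only if it is added to the log. It does not help after SD15, where tapering rests on the concomitant-medication log.

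All endpoints are exploratory (SAP 4.1), and daily doses are plotted per patient (SAP 12.1), so a false plateau might be noticed. That limits the seriousness, but no step tells anyone to act on what the plot shows.

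Three stronger readings are tempting. The first is that the taper results are wrong; without the count of partial dates, the documents cannot support that. The second is that the rule favours the drug. It does not do so consistently: overlap after SD0 delays taper, while an inflated SD0 reference or pre-MAS target eases it. The third is that SAP 9.6 contradicts the errata by saying "Missing dates will not be replaced". That sentence concerns classifying medications as prior or concomitant, not the dose derivation.

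**Conclusion.** The concern holds in conditional form. The stated rule ignores known dates in the same patient, and where a partial stop precedes a known later step it gives a wrong daily dose, whether overlaps are summed or the maximum is taken. The best-supported consequence is a delayed or cancelled taper after SD15: in a 30-day month, 14.5 days of stretch on average and 29 at most for a month-only stop, and much longer for a year-only stop. The easier 50% target arises only if steps overlap at SD0 and are summed. The inflated pre-MAS target arises only for a patient on route (i), with a partial start on the MAS steroid, the dose read from the derived series, and no fallback.

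The realised size is unknown. Each patient misclassified moves a proportion by 8.3 points of 12. With descriptive, exploratory endpoints this is not fatal, but it should be corrected before database lock.

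**What to change.** Amend errata 6.1.8 for glucocorticoids only.

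- (a) Cap an imputed stop at the day before the next glucocorticoid step when that start is fully known and the records are sequential steps, including a switch of drug.
- (b) Do not let an imputed start precede the known stop of the preceding step, or the MAS diagnosis date when the recorded indication is MAS only. The errata change to 9.6 concedes that "The investigators may record either sJIA or MAS (or both) as indication for their use", so list records marked both or unclear for review before database lock.
- (c) Where adjacent dates are both partial, a cap would rest on another imputed date. Do not sum the overlapping steps, and use the daily log for SD-3 to SD15.
- (d) List every patient whose taper flag or taper date depends on an imputed date, and repeat the taper analyses under the opposite imputation (latest start, earliest stop). Where both dates of a record are partial in the same month, that re-run would put the stop before the start, so resolve such records by hand.

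Keep year-only maintenance records: a start moved to 1 January of an earlier year usually leaves the pre-MAS dose unchanged.

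In the known-next-start example, (a) returns permanent taper to SD7. In the pre-MAS example, (b) returns 0.2 mg/kg/day. The all-partial example is not repaired by a cap and would appear in the listing under (d).

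The cost is errata wording, a little programming, and some manual review of partial-date records.

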## **List of Abbreviations**

Abbreviation	Definition
AE	adverse event
AOSD	adult onset Still's disease
ATC	anatomical therapeutic chemical
BSA	body surface area
CSR	clinical study report
DOB	date of birth
Eudra CT	European Union Drug Regulating Authorities Clinical Trials Database
GCP	Good Clinical Practice
GDPR	general data protection regulation
HLGT	high level group term
HLH	hemophagocytic lymphohistiocytosis
ICH	International Council for Harmonisation of Technical Requirements for Pharmaceuticals for Human Use
IRR	infusion related reactions
LLOQ	lower limit of quantification
MAS	macrophage activation syndrome
MedDRA	medical dictionary for regulatory activities
SAP	statistical analysis plan
SD	study day

AD-ST-33.06 Effective date: 12-Nov-2020

Version 2.0 | Date 22-Jul-2021 | AD-PR-109.02 Effective date: 17-Aug-2020 Page 17 of 18

Abbreviation	Definition
SOC	system organ class
sJIA	systemic juvenile idiopathic arthritis
TEAE	treatment-emergent adverse event
ULOQ	upper limit of quantification
WHO-DD	world health organization drug dictionary

[figure not shown]
